#### **10 RISK / BENEFIT ASSESSMENT**

- Anticipated risks. Describe the reasonably foreseeable risks of harm, discomforts, and hazards to the subjects and others of the research procedures. For each harm, discomfort, or hazard:
  - Describe the magnitude, probability, duration, and/or reversibility of the harm, discomfort, or hazard, AND
  - Describe how the risks will be reduced or managed. Do not describe data security protections here, these are already described in Question 9.6.
  - Consider possible physical, psychological, social, legal, and economic harms, including possible negative effects on financial standing, employability, insurability, educational advancement or reputation. For example, a breach of confidentiality might have these effects.
  - Examples of "others": embryo, fetus, or nursing child; family members; a specific group.
  - Do not include the risks of non-research procedures that are already being performed.
  - If the study design specifies that subjects will be assigned to a specific condition or intervention, then the condition or intervention is a research procedure even if it is a standard of care.
  - Examples of mitigation strategies: inclusion/exclusion criteria; applying appropriate data security measures to prevent unauthorized access to individually identifiable data; coding data; taking blood samples to monitor something that indicates drug toxicity.
  - As with all questions on this application, you may refer to uploaded documents.

Phase 1 Data Analysis Activities & Phase 2 MRTs: Participants will be all consumers who naturalistically engaged with MHA and/or TS over the past 2 years (2018-2020)(Phase 1) and who naturalistically engage during the study (Phase 1 and 2). We do not anticipate any risks as participants will be consuming services from MHA and TS as they typically would.

Phase 1 & Phase 2 Focus Groups: Participants may experience fatigue during the focus groups. They will be able to take breaks and/or stop participating at any time. Video recording of participants may cause some stress for participants and presents a risk of loss of confidentiality. They will be informed prior to joining that they can to turn off their video camera at any time. Video recordings will be stored securely and only accessible to researchers. Data from focus groups will be coded and analyzed by study team members resulting in deidentified outputs.

Phase 1 Talkspace Survey: Participants may experience fatigue while responding to the survey. They will be able to take breaks and/or stop participating at any time.

Phase 3B Study 1 SMART: Participants may experience emotional distress and/or discomfort while engaging with survey questions or reading content on the MHA website. When scoring positively on questions regarding suicidality on the PHQ-9, MHA provides the following message to users: If you need immediate help, you can reach the Suicide & Crisis Lifeline by calling or texting **988** or using the chat box at **988lifeline.org**. You can also **text "MHA" to 741-741** to reach the Crisis Text Line. **Warmlines** are an excellent place for non-crisis support. There is also a 'contact us' feature on the MHA website that allows users to contact organization staff with questions.

Phase 3B Study 2: Some of the questions/prompts asked during assessments or when engaging with the DIY tool might make participants feel uncomfortable or upset; however, participants may choose not to answer any question at any time and still continue with the study. They are also informed during consent that if experiencing emotional distress and/or thoughts of self-harm or suicide, to text MHA to 741741 or call or text 988 to be connected to immediate help.

Document Date & Version 06/26/2020 Version 2.4 Participants may experience fatigue while responding to the survey. They will be able to take breaks and/or stop participating at any time.

If the participant endorses any suicidal ideation during the PHQ-9 administration in REDCap, they will see the following information on the screen in REDCap: "If you are ever experiencing thoughts that life is not worth living, self-harm, or suicide and need to speak with someone immediately, you can reach the Suicide & Crisis Lifeline by calling or texting 988 or using the chat box at 988lifeline.org/chat. You can also text "MHA" to 741-741 to reach the Crisis Text Line."

10.2 Reproductive risks. Are there any risks of the study procedures to men and women (who are subjects, or partner of subjects) related to pregnancy, fertility, lactation or effects on a fetus or neonate?

Examples: direct teratogenic effects; possible germline effects; effects on fertility; effects on a woman's ability to continue a pregnancy; effects on future pregnancies.

Х	No
	Yes

 $\rightarrow$  If no go to question 10.3 No

- → If yes, answer the following questions:
  - a. Risks. Describe the magnitude, probability, duration and/or reversibility of the risks.

b. Steps to minimize risk. Describe the specific steps that will be taken to minimize the magnitude, probability, or duration of these risks.

Examples: inform the subjects about the risks and how to minimize them; require a pregnancy test before and during the study; require subjects to use contraception; advise subjects about banking of sperm and ova.

If the use of contraception will be required: describe the allowable methods and the time period when contraception must be used.

c. Pregnancy. Describe what will be done if a subject (or a subject's partner) becomes pregnant

For example; will subjects be required to immediately notify study staff, so that the study procedures can be discontinue or modified, or for a discussion of risks, and/or referrals or counseling?

- 10.3) MRI risk management. Answer this question only if the subjects will receive MRI scans. A rare but serious adverse reaction called nephrogenic systemic fibrosis (NSF) has been observed in individuals with kidney disease who received gadolinium-based contrast agents (GBCAs) for the scans. Also, a few healthy individuals have a severe allergic reaction to GBCAs.
  - a. Describe how the renal function of subjects will be assessed prior to MRI scans and how that information will be used to exclude subjects at risk for NSF.

1	١.,
rı/	- 24
11/	u

	e protocol for handling a severe allergic reaction to the GBCA or any other medical rgency during the MRI scan, including who will be responsible for which actions.
n/a	
Unforeseeabl	e risks. Are there any research procedures that may have risks that are currently unforeseeable?
Example: using	a drug that hasn't been used before in this subject population.
X No	
Yes	→ If yes, identify the procedures.
patients are u	will be under regional or general anesthesiology. Will any research procedures occur while nder general or regional anesthesia, or during the 3 hours preceding general or regional anesthesia non-research reasons)?  → If yes, check all the boxes that apply.
	Administration of any drug for research purposes
	Inserting an intra-venous (central or peripheral) or intra-arterial line for research purposes
	Obtaining samples of blood, urine, bone marrow or cerebrospinal fluid for research purposes
	Obtaining a research sample from tissue or organs that would not otherwise be removed during surgery
	Administration of a radio-isotope for research purposes**
	Implantation of an experimental device
	Other manipulations or procedures performed solely for research purposes (e.g., experimental liver dialysis, experimental brain stimulation)
	If any of the boxes are checked: Provide the name and institutional affiliation of a physician anesthesiologist who is a member of the research team or who will serve as a safety consultant about the interactions between the research procedures and the general or regional anesthesia of the subject-patients. If the procedures will be performed at a UW Medicine facility or affiliate, the anesthesiologist must be a UW faculty member, and the Vice Chair of Clinical Research in the UW Department of Anesthesiology and Pain Medicine must be consulted in advance for feasibility, safety and billing.

\*\* If the box about radio-isotopes is checked: the study team is responsible for informing in advance all appropriate clinical personnel (e.g., nurses, technicians, anesthesiologists, surgeons) about the administration and use of the radio-isotope, to ensure that any personal safety issues (e.g., pregnancy) can be appropriately addressed. This is a condition of IRB approval.

10.6 Data and Safety Monitoring. A Data and Safety Monitoring Plan (DSMP) is required for clinical trials (as defined by NIH). If required for this research, or if there is a DSMP for the research regardless of whether it is required, upload the DSMP to Zipline. If it is embedded in another document being uploading (for example, a Study Protocol) use the text box below to name the document that has the DSMP. Alternatively, provide a description of the DSMP in the text box below.

The DSMP has been uploaded to Zipline as "MHATS DSMP"

10.7 Un-blinding. If this is a double-blinded or single-blinded study in which the participant and/or relevant study team members do not know the group to which the participant is assigned: describe the circumstances under which un-blinding would be necessary, and to whom the un-blinded information would be provided.

n/a

10.8 Withdrawal of participants. If applicable, describe the anticipated circumstances under which participants will be withdrawn from the research without their consent. Also, describe any procedures for orderly withdrawal of a participant, regardless of the reason, including whether it will involve partial withdrawal from procedures and any intervention but continued data collection or long-term follow-up.

n/a

(10.9) Anticipated direct benefits to participants. If there are any direct research-related benefits that some or all individual participants are likely to experience from taking part in the research, describe them below:

Do not include benefits to society or others, and do not include subject payment (if any). Examples: medical benefits such as laboratory tests (if subjects receive the results); psychological resources made available to participants; training or education that is provided.

n/a

#### 10.10 Return of individual research results.

In this section, provide your plans for the return of individual results. An "individual research result" is any information collected, generated or discovered in the course of a research study that is linked to the identity of a research participant. These may be results from screening procedures, results that are actively sought for purposes of the study, results that are discovered unintentionally, or after analysis of the collected data and/or results has been completed.

See the **GUIDANCE Return of Individual Results** for information about results that should and should not be returned, validity of results, the Clinical Laboratory Improvement Amendment (CLIA), consent requirements and communicating results.

a. Is it anticipated that the research will produce any individual research results that are clinically actionable?

"Clinically actionable" means that there are established therapeutic or preventive interventions or other available actions that have the potential to change the clinical course of the disease/condition, or lead to an improved health outcome.

In general, every effort should be made to offer results that are clinically actionable, valid and pose life-threatening or severe health consequences if not treated or addressed quickly. Other clinically actionable results should be offered if this can be accomplished without compromising the research.

No

Yes	
 
→ If yes, answer the following questions (a.1-a.3).
 
a.1. Describe the clinically actionable results that are anticipated and explain which results, if any, could be urgent (i.e. because they pose life-threatening or severe health consequences if not treated or addressed quickly).
 

	Examples of urgent results include very high calcium levels, highly elevated liver function test results, positive results for reportable STDs.
	a.2. Explain which of these results will be offered to subjects.
	a.3. Explain which results will not be offered to subjects and provide the rationale for not
	offering these results.  Reasons not to offer the results might include:  There are serious questions regarding validity or reliability  Returning the results has the potential to cause bias  There are insufficient resources to communicate the results effectively and appropriately  Knowledge of the result could cause psychosocial harm to subjects
	Knowledge of the result codia eduse psychosocial harm to subjects
-	
 
Ian for offering subjects any results that are not clinically actionable?
 
on-actionable genetic results, clinical tests in the normal range, experimental and/or uncertain results.
 
→ If yes, explain which results will be offered to subjects and provide the rationale for offering these results.
 

c. Describe the	e validity and reliability of any results that will be offered to subjects.
	consider evidence of validity such as studies demonstrating diagnostic, prognostic, or predictive value, matory testing, and quality management systems.
n/a	
the descrip	e process for communicating results to subjects and facilitating understanding of the results. In tion, include who will approach the participant with regard to the offer of results, who will ate the result (if different), the circumstances, timing, and communication methods that will be
n/a	
	y plans to share results with family members (e.g. in the event a subject becomes ed or deceased).
n/a	
	ox to indicate that any plans for return of individual research results have been described in the manner to provide results to participants, this should be stated in the manner.

Document Date & Version 06/26/2020

See the  $\underline{\textit{GUIDANCE Return of Individual Results}}$  for information about consent requirements.

	Confirmed
10.11 Commercial pr	oducts or patents. Is it possible that a commercial product or patent could result from this
study?	
X No	
Yes →	If yes, describe whether subjects might receive any remuneration/compensation and, if yes, how the amount will be determined.

#### 11 ECONOMIC BURDEN TO PARTICIPANTS

11.1 Financial responsibility for research-related injuries. Answer this question only if the lead researcher is not a UW student, staff member, or faculty member whose primary paid appointment is at the UW.

For each institution involved in conducting the research: Describe who will be financially responsible for research-related injuries experienced by subjects, and any limitations. Describe the process (if any) by which participants may obtain treatment/compensation.

n/a

11.2 Costs to subjects. Describe any research-related costs for which subjects and/or their health insurance may be responsible (examples might include: CT scan required for research eligibility screening; co-pays; surgical costs when a subject is randomized to a specific procedure; cost of a device; travel and parking expenses that will not be reimbursed).

Phase 1 & Phase 2: MHA services are free. TS consumers pay for their services. Because this phase examines data from consumers who are naturalistically engaged in MHA and TS services, TS consumers will continue to pay for their services.

11.3 Reimbursement for costs. Describe any costs to subjects that will be reimbursed (such as travel expenses).

N/A

#### **12 RESOURCES**

- (12.1) Faculty Advisor. (For researchers who are students, fellows, or post-docs.) Provide the following information about the faculty advisor.
  - Advisor's name
  - Your relationship with your advisor (for example: graduate advisor; course instructor)
  - Your plans for communication/consultation with your advisor about progress, problems, and changes.

N/A

12.2 UW Principal Investigator Qualifications. Upload a current or recent Curriculum Vitae (CV), Biosketch (as provided to federal funding agencies), or similar document to the Local Site Documents page in Zipline. The purpose of this is to address the PI's qualifications to conduct the proposed research (education, experience, training, certifications, etc.).

For help with creating a CV, see http://adai.uw.edu/grants/nsf\_biosketch\_template.pdf and https://education.uwmedicine.org/student-affairs/career-advising/year-4/residency-applications/curriculum-vitae/

Document Date & Version 06/26/2020

Researcher Date & Version

X The CV will be uploaded.

12.3 UW Study team qualifications. Describe the qualifications and/or training for each UW study team member to fulfill their role on the study and perform study procedures. (You may be asked about non-UW study team members during the review; they should not be described here.) You may list these individuals by name, however if you list an individual by name, you will need to modify this application if that individual is replaced. Alternatively, you can describe study roles and the qualifications and training the PI or study leadership will require for any individual who might fill that role. The IRB will use this information to assess whether risks to subjects are minimized because study activities are being conducted by properly qualified and trained individuals.

Describe: The role (or name of person), the study activities they will perform, and the qualifications or training that are relevant to performing those study activities.

#### **Examples:**

Research Study Coordinator: Obtain consent, administer surveys, blood draw. Will have previous experience coordinating clinical research and be a certified phlebotomist in WA.

Undergraduate Research Assistant: Obtain consent, perform all study procedures. Will have had coursework in research methods, complete an orientation to human subjects protections given by the department, and will receive training from the PI or the graduate student project lead on obtaining consent and debriefing subjects. Acupuncturist: Perform acupuncture procedures and administer surveys. Must be licensed with WA State DoH and complete training in administering research surveys given by the project director, an experienced survey researcher.

Co-Investigator: Supervise MRI and CT scan procedures and data interpretation, obtain consent. MD, specialty in interventional radiology and body imaging. 5-years clinical research experience.

Project Manager: 4+ years experience in clinical research, remote clinical trials, and data acquisition; Responsible for coordinating all data collection activities, documenting study procedures, preparing study reports and ensuring regulatory requirements are met.

Graduate Student: Conduct data analyses and machine learning experiments on existing observational data of MHA and TS platforms

Data Analyst: Assist PIs in setting up the data management platform, code book, monitoring data quality, communicating with MHA and TS regarding technical issues, and generating reports on data quality Research Study Assistant: Provide operational support to all facets of the study

12.4 Study to	eam training and communication. Describe how it will be ensured that each study team member is
adequat	tely trained and informed about the research procedures and requirements (including any changes) as
well as t	heir research-related duties and functions.
Γ	There is no study team.

All study team members have completed CITI trainings. The study team will meet regularly (biweekly at project start up and monthly thereafter).

### 13 OTHER APPROVALS, PERMISSIONS, and REGULATORY ISSUES

	ns. Identify any other approvals or permissions that will be obtained. For example: from anization, funding agency, employee union, UW Medicine clinical unit.
Do not attach the approvals	and permissions unless requested by the IRB.
N/A	
	est. Does any UW member of the team have ownership or other Significant Financial earch as defined by UW policy GIM 10 ?
X No Yes → If yes, has the proposed re No	ne Office of Research made a determination regarding this SFI as it pertains to the search?  If no, contact the Office of Research [contact], [contact]) for guidance on how to obtain the determination
Yes	→ If yes, upload the Conflict Management Plan for every UW team member who has a FCOI with respect to the research, to Zipline . If it is not yet available, use the text box to describe whether the Significant Financial Interest has been disclosed already to the UW Office of Research and include the FIDS Disclosure ID if available.

ENHANCING ENGAGEMENT WITH DIGITAL MENTAL HEALTH CARE

STUDY00010958

07/03/2024

NCT04507360

Aim 3B Statistical Analysis Plan. For Study 1, all research questions were examined via logistic regressions. We assessed whether participants' first condition (i.e., demographics survey or Next Steps survey) predicted the odds of disengagement. Within participants who completed the demographics survey, we examined whether the odds of disengaging and clicking a featured resource on the screening results page significantly differed for participants in the Tailored Resources to Demographics condition compared to control (i.e., Generic Response + Generic Resources). Within participants from the Next Steps survey condition, we tested whether engagement significantly differed for participants shown Tailored Response + Generic Resources, Generic Response + Tailored Resources to Desired Resources, and Tailored Response + Tailored Resources to Desired Resources compared to control. We aimed to identify the optimal tailoring strategy by comparing engagement across all tailoring conditions, with Tailored Resources to Demographics set as the reference group. For Study 2, research questions were examined via t-tests and Cohen's d effect sizes comparing engagement, short-term restructuring effectiveness, longer-term effectiveness (e.g., skill acquisition, reductions in depression and anxiety), and heterogeneous treatment effects by condition (i.e., control, DIY tool without AI, and DIY tool with AI).

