5. Ability to conduct micro-randomized trials and SMART trials of engagement strategies. Both MHA and TS continuously conduct marketing-based research to improve their outreach and engagement of consumers with mental health needs. MHA conducts experimental user testing on engagement such as modifying tone, placement, and medium (written vs audio) of education materials, modifying language and linkages to services like telehealth partners, adding relevant links to other materials, and improving the formatting of articles for clarity. These efforts reduced the bounce rate (the rate at which users leave a page without taking any further actions on the site) for edited pages from 91% to 68% on average, and increased the average time spent on the site during a session by 15%. MHA has conducted microtrials evaluating user experiences comparing algorithm-driven resource selection to manually selected resources, and found users prefer manually selected resources. These tests have used simple pre-post manipulation of website materials; the current grant proposal would provide funding for more complex, causal design testing using MRTs and SMART methods. The goal of the projects is to understand what level of engagement users in the earliest stages of recovery are willing to engage in and what factors might increase utilization of high investment services. TS has similarly designed and tested onboarding and treatment engagement strategies that seek to 1) increase likelihood of beginning treatment, and 2) increase the likelihood of treatment completion. Onboarding strategies include modifying informational pages with different media (testimonials, therapist background information, patient education and self-assessment materials, an interactive chatbot experience, etc.), therapy benefits, financial incentives, and calls to action. Once individuals begin treatment, TS shifts effort to improving treatment completion rates by providing therapist match recommendations, collecting and reporting outcomes to users and therapists, integrating evidence-based exercises/worksheets in an interactive interface, and providing feedback to therapists regarding user engagement and pacing of therapy.

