## **Randomization sequence**

The drafted randomization sequence is outlined on the MHA SMART Flow.pdf uploaded to zipline. Participants will be randomized first between a standard demographics survey to start or demographics along with a mini quiz focusing on asking a participant's primary website action intention (e.g., reading more about depression, connecting with therapists, using a DIY tool) and perceived need to do something to improve their mental health. Participants will then be randomized to types of screening results pages, with combinations of tailored responses and resources based on their responses to the demographics quiz and/or the mini quiz. For instance, if the participant chooses to continue to visit further content, they will be randomized to conditions of different presentations of a DIY question or tool on the page. Length of engagement, bounce rates, and other variables listed under metadata collection will be used to examine the impact of tailoring on engagement, which conditions and combinations of conditions result in increased engagement, and how the use of DIY tools impact engagement.

## Study 2

As previously proposed in Aim 3, we have developed an AI tool that uses machine learning / NLP / AI methods to personalize and tailor an intervention to improve engagement and completion outcomes. We focus on a specific, popular DIY tool (~10,000 users /month) that teaches cognitive restructuring. Our pilot work found that (1) engagement and completion rates on DIY tools can be low, and (2) a pilot AI tool had significantly higher engagement and completion rates. These differences may arise due to AI support, UI/UX/design differences, other factors, or a combination thereof. Additionally, the efficacy of the digital tool to improve mental health functioning is unknown. Study 2 will recruit 300 participants who will be randomly assigned to one of three groups for a longitudinal month-long study: twice-weekly DIY tool use with AI, without AI, or a control group.

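### The four Next Steps conditions form a complete 2x2, but no planned analysis estimates what tailoring both response and resources adds over tailoring one of them.

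*SAP*

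**What the plan says.** The Study 1 part of the SAP is one paragraph, in which "all research questions were examined via logistic regressions". Its demographics sentence defines the comparator as "control (i.e., Generic Response + Generic Resources". For the other survey arm it continues: "Within participants from the Next Steps survey condition, we tested whether engagement significantly differed" for "Tailored Response + Generic Resources, Generic Response + Tailored Resources to Desired Resources, and Tailored Response + Tailored Resources to Desired Resources", each against control. That sentence does not define control again. Because it is limited to Next Steps participants, I read control there as the generic/generic cell of the same arm.

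A last step looks for the best way to tailor by "comparing engagement across all tailoring conditions, with Tailored Resources to Demographics set as the reference group". No factor coding, main effect, interaction, or direct contrast among the Next Steps tailored cells is mentioned.

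Protocol section 5.1 (Randomization sequence) describes results pages that combine tailored responses with tailored resources. It says the data will show, among other things, "which conditions and combinations of conditions result in increased engagement".

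**The concern.** Write each condition as response/resources, G for generic and T for tailored. The Next Steps arm then holds G/G (control), T/G, G/T and T/T.

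The planned contrasts are T/G, G/T and T/T, each against G/G. The first two show what each element does with the other generic. The third shows the joint effect of both. None shows whether adding the second element improves on having one.

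The final comparison does not fill that gap. Its reference cell belongs to the demographics-survey arm, so each contrast between it and a Next Steps cell mixes the survey received with the tailoring.

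At stake is the practical recommendation. If T/T does no better than T/G or G/T, the simpler page would serve as well, and the planned tests are not built to show this.

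**Working it through.** **Plan's own figure.** There is none to reproduce. The documents give no power, effect size, alpha or sample-size calculation for Study 1.

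**Inputs.**
- Total: 50,000 expected users (Protocol 5.1, Phase 3, Study 1).
- Allocation: no ratio stated at either stage. Assuming 1:1 and then equal across four cells, 50,000 / 2 / 4 = 6,250 per cell. A total of 10,000 would give 1,250.
- Two-sided 5% level and 80% power: assumed.
- Control engagement rate: not stated; 5% to 68% taken as a range.

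**Step 1: which comparisons are planned.**

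| Question | Contrast | Planned? |
|---|---|---|
| Response, resources generic | T/G v G/G | yes |
| Resources, response generic | G/T v G/G | yes |
| Both against neither | T/T v G/G | yes |
| Resources, response already tailored | T/T v T/G | no |
| Response, resources already tailored | T/T v G/T | no |
| Interaction | (T/T - T/G) - (G/T - G/G), log odds | no |

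**Step 2: standard errors.** The variance of one cell's log odds is v = 1/(n p (1 - p)). With n = 6,250 and p = 0.20, v = 1/(6,250 x 0.16) = 0.001.
- Single contrast, including T/T v T/G: sqrt(2v) = 0.045.
- Main effect (average of two single contrasts on separate cells): sqrt(4v/4) = sqrt(v) = 0.032.
- Interaction: sqrt(4v) = 0.063.

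Main effect over single contrast is 1/sqrt(2) = 0.71, about 29% smaller.

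**Step 3: detectable difference at 80% power.** Solved from the two-proportion test with pooled variance. The contrast is 6,250 v 6,250; the main effect is 12,500 v 12,500.

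| Control rate | Single contrast | Main effect |
|---|---|---|
| 5% | 1.15 points | 0.80 points |
| 20% | 2.04 | 1.44 |
| 50% | 2.50 | 1.77 |
| 68% | 2.31 | 1.64 |

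If an element's effect is the same at both levels of the other, and just large enough for 80% power on the main effect, a single contrast has about 51% power. For 20% v 22%, 6,510 are needed per compared group: 4 x 6,510 = 26,040 in the arm with single contrasts, or 2 x 6,510 = 13,020 with main effects. At a total of 10,000 the single contrasts detect about 2.7 to 5.6 points.

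**Step 4: what the planned tests would show.** Take 6,250 per cell, G/G at 20%, and a log-odds effect of 0.12 for each element alone, so T/G and G/T are both 21.99%.
- *Combining adds nothing* (T/T also 21.99%): each control contrast has 78% power. The likely reading is that all three work, and nothing planned addresses the lack of added benefit.
- *Effects add on the log-odds scale* (T/T 24.12%): T/T v T/G would have about 81% power, but it is not planned.
- An interaction of 0.12 in either direction would be detected with only about 50% power.

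**The case against.** Four objections have force.

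**The combination and the components are tested.** A reader might infer that the trial never tests whether combining helps, or cannot say which element works. The SAP does not support either reading. T/T is compared with control and also enters the final comparison; T/G and G/T against control isolate each element. What is missing is the increment of T/T over one element.

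**Effects against control are a legitimate target.** A reader might infer that half the data are thrown away for each factor. The T/T data are used in their own contrast, and sharing one control cell is normal in many-to-one comparisons. The precision gain applies only if average effects are wanted, and averages can mislead when the factors interact.

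**Adding an interaction does not by itself gain precision.** A model with both factors and their interaction fits exactly as a four-level condition variable does. Under reference coding its two main-effect coefficients are simply T/G v G/G and G/T v G/G, with the same standard errors. The gain needs effect coding.

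**The protocol link is loose.** The documents never call the design factorial. The randomisation flow file is not included. The word combinations could mean sequences of survey, results page and DIY presentation. That is fair, but the SAP's own aim of finding the best strategy still calls for comparing the combined page with the simpler ones.

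A reader might also treat the bounce rate in Protocol 1.8b, item 5 as the share lost before the results page, and so shrink the cells sharply. That figure is a fall "for edited pages from 91% to 68% on average" in MHA's earlier user testing. Nothing ties it to users who start the PHQ-9, so it gives no basis for cell sizes here.

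**Conclusion.** The point holds as a gap in the analysis, not an error in the planned tests. The Next Steps arm randomises a complete 2x2, and the SAP leaves out the within-arm comparisons that show what the combination adds.

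The precision cost is secondary and modest if 50,000 is reached: about 1.2 to 2.5 detectable points with single contrasts, against 0.8 to 1.8 with averaged main effects. These figures rest on equal allocation, a two-sided 5% level, 80% power and control rates of 5% to 68%, none of which the documents state. The structural gap depends on none of them. It depends only on reading control in the Next Steps sentence as that arm's generic/generic cell.

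**What to change.** In the Next Steps arm:

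1. Fit one logistic model with response and resources effect-coded (-1/2 for generic, +1/2 for tailored) and their product. Each factor's coefficient is then its log odds ratio averaged over the other factor, and the product's coefficient is the interaction.
2. Report both main effects and the interaction with confidence intervals.
3. Add T/T v T/G and T/T v G/T, and draw on them when naming the best strategy.
4. Keep the three planned contrasts with control.
5. The SAP is written in the past tense, so state for each added analysis when it was specified.

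The cost is a few sentences and one re-parameterised model on data already planned. It adds five estimates per outcome (two main effects, one interaction, two contrasts). The interaction is the least precise (0.063 against 0.045 for a single contrast at a 20% rate), so it should be read through its interval, and a non-significant result should not be taken as proof that the effects simply add.
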